- Since March 2015, an open-label pilot trial on the acute treatment of migraine using the Cefaly® device has been underway at Columbia University, NY. Patients experiencing a migraine attack for at least 3 hours (without use of acute medications during this time) and having stable pain intensity for at least 1 hour, are eligible to receive a 60-minute stimulation to treat their attack. Pain is assessed on a 10-point visual analogue scale (VAS) before, after the 1-hour treatment, and 2 hours after the beginning of the treatment. The study is still on-going, but the results to date confirm prior observations that e-TNS therapy via the Cefaly® device can significantly reduce pain intensity during an acute migraine attack, as measured via the VAS.

Based on the data from the above studies and preliminary findings from the open-label pilot trial at Columbia, it is reasonable to further investigate the efficacy of e-TNS with the Cefaly® device as an acute treatment for migraine via a double-blind, randomized, sham-controlled trial.

2. Study objective

The main objective of this study is to assess the efficacy of the Cefaly® device as an acute treatment of migraine attack in adult patients.

3. Study outcomes

Primary outcome:

- Mean change of pain score at 1 hour compared to baseline

Secondary outcomes:

- Proportion of patients not having required rescue medication at 2 hours
- Mean change of pain score at 2 hours compared to baseline (if rescue therapy was not used)
- Proportion of patients not having required rescue medication within 24 hours
- Mean change of pain score at 24 hours compared to baseline (if rescue therapy was not used)

4. Study design

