4.2.3. Post-treatment phase

Two hours after the beginning of the treatment the patient will have to give a new estimate of the pain on the VAS, provided that the patient didn't take a rescue medication before.

After the 2 hours, if needed usual rescue treatment can be administrated to the patient. If so, this is recorded by the investigator.

Patients will also be instructed to record the pain level 24 hours after the beginning of the treatment. They will be contacted to report this pain level and whether or not rescue medication was taken within the 24 hours following the beginning of the treatment. In case of rescue medication intake within the 24 hours following the treatment the pain level at 24 hours will not be taken into account.

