4.2.4. Drop-outs, intention-to-treat and last value carried forward

a) During the treatment one-hour phase

If the patient takes rescue medication before 1 hour, it is a drop-out because the action of the medication affects the pain estimate at 1 hour.

If the patient stops the one-hour treatment and leaves the clinic, it is a drop-out because there is no pain estimate at 1 hour.

If the device stopped working accidentally, it is a drop-out because of technical reason.

On the other hand, if a patient does not get the full Cefaly acute treatment (does not want to complete the 1 hour stimulation), but stays available for the 2 hours of the protocol, this patient is kept in the trial and considered as an intention-to-treat patient (as opposed to per protocol patient).

b) During the post treatment phase

If the patient takes rescue medication before 2 hours, only the one-hour pain intensity estimate has been measured; the last value carried-forward method will be applied for 2 and 24 hours pain intensity estimate.

If the patient takes rescue medication at 2 hours or after 2 hours, the last value carried-forward will be applied for the 24 hours pain intensity estimate.

[figure not shown]

Figure 1 - Study flowchart

5. Subjects

The study will include 90 men or women.

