6.6. Medication during the trial

No medication can be used during the 2 hours of the study (1 hour of Cefaly stimulation followed by 1 hour of observation). Any rescue medication can be used after these 2 hours and have to be recorded during the 24 hours following the beginning of the treatment.

If a patient wants a rescue medication during the one-hour treatment phase it is a drop-out, if the patient wants a rescue medication after the one-hour treatment phase but before the 2 hours of the study the last value carried-forward is applied.

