7.1. Measures

Pain score. In order to evaluate the modification of pain score from baseline to 1-hour treatment and to 2-hour treatment, patients will be asked to give an indication on the pain level using a visual analogue scale (VAS) counting eleven levels (0 = no pain, 10 = maximum pain) at the recruitment phase (before applying the treatment), right after the treatment phase (1 hour), 2 hours after the beginning of the treatment and at 24 hours after the beginning of the treatment.

Rescue medication after the treatment. The investigator will also record whether the patient uses another acute medication right after the 2 hours. Patients will also be contacted 24 hours after the beginning of the treatment to report whether or not rescue medication was taken within the 24 hours following the beginning of the treatment.

The following table depicts when the different measures will be made:

	Baseline	1 hour	2 hours	24 hours
Pain score	●	●	●	●
Rescue medication intake			●	●

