8.2. Statistics

8.2.1. Sample size

Results from a randomized controlled trial on an acute migraine treatment (6) showed in the placebo group a reduction in mean pain score of 10% after 1 hour and 14% after 2 hours, compared to baseline. The results of the pilot trial on the acute treatment of migraine using the Cefaly® device showed a reduction in mean pain score of 59% after 1 hour and 55% after 2 hours. The standard deviation related to mean pain score was 2.42 after 1 hour and after 2 hours. Based on these results we could assume a difference in mean pain score of 2.83 after 1 hour and 2.40 after 2 hours between the active and placebo groups. A minimum of 17 patients in each group would be statistically required to detect a significant difference in mean pain score after 1 hour and after 2 hours, with a power of 80% and at two-sided alpha level of 5%, using a t-test for two independent samples.

A previous study reported 71% of patients from the placebo group using rescue medication compared to 41.33% for active groups on average (7). Considering these percentages, 43 patients in each group would have been statistically required to detect a significant difference in rescue medication use after 24 hours with a power of 80% and at two-sided alpha level of 5%, using a proportion test for two independent samples.

Overall, at least 43 patients in each group should allow to detect a significant difference between active and placebo groups in mean pain score after 1 hour and after 2 hours, and in rescue medication use. As the trial will be conducted in three different centres, the number of patients is rounded to 45 in each group (i.e. 15 patients per group and per centre). Consequently, 90 patients will be recruited.

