8.2.2. Statistical methods

- All relevant general, safety and efficacy data will be descriptively summarized at each time point.
- Continuous data will be summarized by the number of subjects (N), the arithmetic mean, the standard deviation, the coefficient of variation as a percentage (CV%), the median, the inter-quartile range, the minimum and the maximum value.
- Categorical data will be summarized by absolute (N) and relative (%) frequency tables.
- Where considered as relevant, the study data will also be graphically depicted.

- Imputation of missing data will be performed according to the last value carried forward method.
- Analyses will be conducted on an intent-to-treat (ITT) basis, i.e. including all subjects who used the study device for more than 4 minutes (see in exclusion criteria 8. Allodynia), did not take rescue medication before the 1 hour and reported pain at 1 hour.
- A sub-analysis of the per-protocol patients (those receiving the complete 1-hour treatment) will be performed as well.

9. Management of adverse events

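### Read as written, the unrestricted carry-forward rule scores an unreached patient with no rescue at 2 hours as rescue-free at 24 hours, on the secondary outcome that sets the sample size

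*Combined protocol and SAP*

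**What the plan says.** The general rule in section 8.2.2 is "Imputation of missing data will be performed according to the last value carried forward method". It carries no restriction to an outcome or visit.

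Section 3 lists, as a secondary outcome, "Proportion of patients not having required rescue medication within 24 hours". Not taking rescue is the favourable result.

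The table in section 7.1 shows rescue intake measured at 2 hours and 24 hours only. For the first of these, "The investigator will also record whether the patient uses another acute medication right after the 2 hours". For the second, section 4.2.3 relies on contacting the patient: "They will be contacted to report this pain level and whether or not rescue medication was taken within the 24 hours". Section 6.6 adds that "No medication can be used during the 2 hours of the study".

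The specific carry-forward text in section 4.2.4 deals with patients who have taken rescue, and with their pain scores. After rescue before 2 hours, "the last value carried-forward method will be applied for 2 and 24 hours pain intensity estimate"; after later rescue, only the 24-hour pain score is carried. Section 6.6 repeats the rule for rescue between 1 and 2 hours. Neither section says what happens when the rescue report itself is missing.

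The analysis set in 8.2.2 requires a 1-hour pain score but no 24-hour report, so unreached patients stay in the denominator.

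**The concern.** The 24-hour rescue outcome is cumulative, and the window in which rescue is freely allowed opens at 2 hours. For a patient who cannot be reached, the only earlier rescue value is the one at 2 hours. If that value is rescue taken, the patient is already a known failure and nothing is imputed. If it is no rescue, carrying it forward declares success for the following 22 hours, none of which were observed.

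So every patient whose 24-hour status is truly unknown becomes a responder. Equal loss in the two arms pulls both rescue rates down in proportion, which shrinks the difference and costs power. Heavier loss under verum produces a false advantage for verum; heavier loss under sham does the reverse.

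The outcome is secondary, but section 8.2.1 takes the trial size from it, and the step from 43 to 45 per group is explained by division across centres, with no allowance for loss.

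**Working it through.** **Inputs from section 8.2.1.** Rescue use is "71% of patients from the placebo group using rescue medication compared to 41.33% for active groups on average". The test is a two-sample proportion test, two-sided 5%, 80% power, with 45 per group recruited.

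**Inputs that are assumptions.** m is the share of 24-hour reports missing, unrelated to the patient's true status. r is the share of eventual rescue users already recorded at 2 hours. The documents give neither.

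**Step 1: the plan's figure.** The plan states that "43 patients in each group would have been statistically required to detect a significant difference in rescue medication use after 24 hours". With mean rate (0.71 + 0.4133)/2 = 0.56165 and pooled variance:

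n = [1.960 √(2 × 0.56165 × 0.43835) + 0.842 √(0.71 × 0.29 + 0.4133 × 0.5867)]² / 0.2967² = 42.7, so 43.

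The figure reproduces. Power is 80.3% at 43 and 82.1% at 45 per group. The 17 per group for pain also reproduces, from the 2-hour difference of 2.40 with SD 2.42 and the t distribution.

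**Step 2: what carry-forward does to a rate.** Only rescue users who are both unreached and not yet recorded at 2 hours are misclassified:

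observed rescue rate = p × [1 − m(1 − r)].

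**Step 3: equal loss, 45 per group.** With m = 10% and r = 0 the factor is 0.90: 0.71 × 0.90 = 63.9% and 0.4133 × 0.90 = 37.2%. The difference is 26.7 points, not 29.7. With r = 0.5 the factor is 0.95: 67.5% and 39.3%, a difference of 28.2 points.

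| Loss in each arm | Power, r = 0 | Power, r = 0.5 |
|---|---|---|
| 0% | 82.1% | 82.1% |
| 5% | 77.4% | 79.8% |
| 10% | 72.4% | 77.4% |
| 20% | 62.3% | 72.4% |

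**Step 4: unequal loss, no true effect.** Take 71% rescue in both arms, with 5% loss in sham and 15% in verum. Error rates are exact enumerations of the pooled z-test at 45 per group; with no loss the two-sided rate is 5.3%.

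- r = 0: 0.71 × 0.95 = 67.5% against 0.71 × 0.85 = 60.4%. The false verum benefit is 7.1 points and the two-sided error 11.1%, of which 10.6 percentage points favour verum.
- r = 0.5: 0.71 × 0.975 = 69.2% against 0.71 × 0.925 = 65.7%. The false benefit is 3.6 points and the error 6.9%.
- Swapping the losses (15% sham, 5% verum) gives the same sizes with the sign reversed, against verum.

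**Step 5: the alternatives at 10% equal loss.** Counting unknown as rescue gives p + m(1 − p): 73.9% and 47.2%, power 74.4%. Using only patients with a 24-hour report (45 × 0.90 = 40.5 per group at the true rates) gives 77.8%.

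Under the 5% sham, 15% verum pattern of step 4, counting unknown as rescue gives a two-sided error of 6.5%, with a false verum benefit in only 1.3%. With the losses swapped it creates a false verum benefit of 0.29 × (0.15 − 0.05) = 2.9 points. At a common rescue rate of 41.33% that becomes 0.5867 × 0.10 = 5.9 points, with a two-sided error of 7.9%, against 7.0% for carry-forward at r = 0.

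**The case against.** The strongest reply is that carry-forward was meant for pain only. Wherever sections 4.2.4 and 6.6 apply it, the trigger is rescue intake, and 4.2.4 names only the pain estimate. Section 3 also lists rescue at 2 hours and within 24 hours as separate outcomes, so the cumulative one arguably has no earlier value to carry. This reading is arguable, but no text states it. The 7.1 table puts rescue intake on one row with a 2-hour and a 24-hour value, and 8.2.2 names no outcome. If the pain-only reading is right, a missing rescue report has no rule at all, and the same clarification is needed.

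The second reply concerns size. A reader might infer from the medication bar in 6.6 that almost nobody has rescue recorded at 2 hours. The documents do not support that: section 4.2 has rescue given at 2 hours if needed, and 7.1 has it recorded then. Those patients are known failures and a missed call changes nothing for them. The r = 0 column is therefore an upper end. This objection stands, and it is why a range is given.

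Third, nothing in the documents points to substantial loss at a single 24-hour contact, or to heavier loss under verum. That also stands: the loss patterns are illustrations.

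Fourth, counting missing as rescue recovers little power and can itself favour verum when sham loss is heavier (step 5). That is a reason not to let it stand alone.

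**Conclusion.** The point holds as a defect in a stated rule, on the wording of 8.2.2: followed literally, it scores an unreached patient with no rescue at 2 hours as a 24-hour success. It should be corrected, but its reach is limited. The outcome is secondary, and the primary 1-hour pain comparison is untouched because the analysis set requires a 1-hour pain score.

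At 45 per group and the plan's rates, 10% equal loss takes power from 82% to between 72% (no rescue user recorded at 2 hours) and 77% (half recorded). With no true effect and loss of 5% in sham and 15% in verum, two-sided type I error goes from about 5% to between 7% (half recorded) and 11% (none recorded). Both the loss rates and the share recorded at 2 hours are assumed.

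A reader might infer that the rule favours the device as such. It does not: equal, uninformative loss works against showing a benefit, and heavier sham loss biases against verum. Nor is the 43 per group miscalculated; it is right for complete data.

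**What to change.** In section 8.2.2, state that carry-forward applies to pain scores only and never to rescue status. Then prespecify, for the 24-hour rescue outcome:

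- a patient with rescue already recorded counts as a failure, whether or not the 24-hour contact succeeds;
- a patient with no 24-hour report and no earlier rescue counts as having used rescue;
- an analysis restricted to patients with a 24-hour report is shown beside it;
- a check varies the assumption about unknown status separately by arm;
- the number of missing 24-hour reports is given by arm.

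The cost is a few sentences and an added table, with no change to conduct or recruitment. The downsides are slightly lower success proportions (at 10% loss, 26.1% rather than 29% in sham and 52.8% rather than 58.7% in verum), little power regained (74.4% against 72.4%, with 77.8% for reported cases), and a possible tilt towards verum if sham loss is heavier. Showing both analyses and the arm-specific check lets the reader see whether the conclusion depends on the unreached patients.

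### The set labelled intent-to-treat removes patients rescued in the first hour, so known failures drop out of the 24-hour rescue endpoint (and of the 2-hour one, depending on how it is read)

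*Combined protocol and SAP*

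**What the plan says.** Section 8.2.2 names one main set for the analyses in general and calls it intent-to-treat. Besides more than 4 minutes of device use, it requires that the patient "did not take rescue medication before the 1 hour and reported pain at 1 hour". The only other set is a per-protocol sub-analysis of patients who completed the hour. Missing data are handled by carrying the last value forward.

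Section 4.2.4(a) says of rescue before 1 hour that "it is a drop-out because the action of the medication affects the pain estimate at 1 hour". Section 6.6 repeats the rule: "If a patient wants a rescue medication during the one-hour treatment phase it is a drop-out". Patients who walk out are treated alike: "If the patient stops the one-hour treatment and leaves the clinic, it is a drop-out".

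Rescue in the second hour is handled differently. Section 4.2.4(b) says: "If the patient takes rescue medication before 2 hours, only the one-hour pain intensity estimate has been measured". The patient stays in, and the 1-hour score is carried forward.

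Section 3 lists two secondary endpoints on rescue: "Proportion of patients not having required rescue medication at 2 hours" and "Proportion of patients not having required rescue medication within 24 hours". Sections 4.2.3 and 7.1 count the 24 hours from the start of treatment.

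The 24-hour comparison drives the trial size. Section 8.2.1 says that "43 patients in each group would have been statistically required to detect a significant difference in rescue medication use after 24 hours", against 17 per group for pain.

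**The concern.** Both conditions in the set definition depend on what happens after a device has been allocated (section 4.2.1), so the set is not intent-to-treat in the usual sense.

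The reason given for removing first-hour rescuers is that the drug disturbs the 1-hour pain score. That can justify leaving them out of the pain analysis. It does not carry over to an endpoint whose outcome is rescue itself, because for that endpoint these patients have an observed result, and it is failure. Nothing in the plan brings them back: the per-protocol set is narrower still, carrying values forward cannot help a patient outside the set, and no failure rule or sensitivity analysis is stated.

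At stake is the rescue-free proportion in each arm, on the endpoint that required the larger sample size.

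**Working it through.** **Inputs.** From section 8.2.1: 24-hour rescue 71% on placebo and 41.33% on active; two-sided 5%, 80% power, two-sample proportion test; 43 per group required, 45 planned. The number rescued in the first hour is not given anywhere. The counts below are assumptions, and every removed patient is taken to be a rescue user.

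**1. The plan's own figure.** With pooled variance under the null and no continuity correction, the mean rate is (0.71 + 0.4133)/2 = 0.5617 and

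n = [1.960·√(2·0.5617·0.4383) + 0.842·√(0.71·0.29 + 0.4133·0.5867)]² / (0.2967)² = 42.7, so 43 per group.

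The stated 43 reproduces. The sample-size arithmetic is not at issue.

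**2. Effect within one arm.** With d first-hour rescuers removed from 45, the rescue-free count is unchanged and the denominator falls. The rescue-free rate is therefore multiplied by 45/(45 − d): 45/44 is +2.3% (relative) for d = 1, and 45/42 is +7.1% for d = 3. Within an arm the error always goes the same way.

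**3. Effect on the 24-hour difference.** Rescue-free rate = 45·(1 − p)/(45 − d), with p = 0.4133 (verum) or 0.71 (sham). The chance of significance is from the pooled z-test at 45 per arm, with binomial outcomes and d rescue users removed. Differences are taken before rounding.

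| Removed (verum, sham) | Verum | Sham | Difference (points) | Chance of significance |
|---|---|---|---|---|
| 0, 0 | 58.7% | 29.0% | 29.7 | 81% |
| 1, 1 | 60.0% | 29.7% | 30.3 | 82% |
| 2, 0 | 61.4% | 29.0% | 32.4 | 86% |
| 0, 2 | 58.7% | 30.3% | 28.3 | 77% |
| 3, 3 | 62.9% | 31.1% | 31.8 | 86% |

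The normal-approximation formula gives 82.1% at 45 per arm with none removed; the binomial calculation gives 81%.

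**4. How often the conclusion changes.** At the plan's rates, significance is gained or lost in 0.7% of trials for (1, 1) and in 4% to 5% for (2, 0), (0, 2) or (3, 3). It can go either way:
- 22/45 against 13/45 rescue-free gives p = 0.052; removing two verum first-hour rescuers (22/43) gives p = 0.033.
- 21/45 against 12/45 gives p = 0.049; removing two sham (12/43) gives p = 0.069.

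These are chosen borderline cases, not typical ones.

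**5. Primary endpoint.** The implied baseline is 2.83/(0.59 − 0.10) = 5.78, so the mean reductions are 0.59·5.78 = 3.41 and 0.10·5.78 = 0.58. Counting early exits as zero change:
- (1, 1): (44/45)·(3.41 − 0.58) = 2.77
- (3, 3): (42/45)·(3.41 − 0.58) = 2.64

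With SD 2.42 and 45 per arm, power stays at 99.9% or above in both cases.

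**6. What the 2-hour endpoint means.** Section 3 does not say whether it is cumulative. Section 4.2 places rescue at the 2-hour point, and section 7.1 has the investigator record medication taken right after the 2 hours. These allow a reading limited to that moment as well as one covering any rescue up to then. The 24-hour endpoint has no such ambiguity.

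**The case against.** The strongest reply is that few patients, if any, will be affected. Section 6.6 bars medication for the 2 hours, the session is supervised, section 5.1 requires pain to have been stable for an hour, and section 4.2.4 keeps patients who stop stimulation but stay. All this stands, and it is why the effect is probably small. But sections 4.2.4 and 6.6 also provide for first-hour rescue, so the plan itself foresees it.

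A second reply is that the set is spelled out in the same sentence as its label, so nobody reading the plan is misled. That is fair for the plan. The label matters more in a later report, where the definition may not travel with it.

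A reader might infer three stronger things that the documents do not support:
- That the 2-hour endpoint certainly loses known failures. That depends on a reading the protocol leaves open.
- That the exclusion favours the device or inflates the false-positive rate. Early rescue mainly on sham would work against the device. With no true difference and equal early rescue, neither arm is favoured.
- That the primary result is compromised. At the assumed effect it is not.

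**Conclusion.** The concern holds for the 24-hour rescue endpoint as written. It holds for the 2-hour endpoint only if that means any rescue from the start of treatment to 2 hours. Every first-hour rescue overstates the rescue-free proportion in its arm. The direction of the effect on the comparison is unknown because no early-rescue rate is given. With one or two patients removed, the difference moves between 28.3 and 32.4 points around 29.7, and the chance of significance between 77% and 86% around 81%.

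These figures rest on the plan's rescue rates, 45 per arm, and the assumption that everyone removed took rescue. Patients who leave without a 1-hour score may not have, so only first-hour rescuers are known failures.

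This should be fixed: it is a clear fault in a stated rule, on secondary endpoints, with a probably small effect. The intent-to-treat label and the accidental-stop rule are lesser points. On the latter, section 4.2.4 makes an accidental stop a drop-out, while section 4.2.2 still collects the 60-minute score and section 8.2.2 would then admit the patient after more than 4 minutes of use.

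**What to change.** 1. In section 8.2.2, analyse 24-hour rescue in all allocated patients who pass the tolerance check, counting rescue before 1 hour as rescue required. Define the 2-hour endpoint as any rescue from the start of treatment to 2 hours and treat it the same way. State that drop-outs under section 4.2.4 also receive the 24-hour contact, which the protocol does not now say. Where rescue status stays unknown, show results under both assumptions.
2. Call the present set modified ITT and report exclusions by arm and reason, including patients who fail the tolerance check after allocation. Two conflicts affect this denominator and must be reconciled: randomisation comes before the check in section 4.2.1 but is described after it in 4.2.2, and the check is 4 minutes in sections 4.2.1, 4.2.2, 6.4 and 8.2.2 but 5 minutes in exclusion criterion 8 of section 5.2.
3. Add a sensitivity analysis of the 1-hour pain score that keeps first-hour rescuers and leavers, for example at zero change from baseline.
4. Separately, reconcile the accidental-stop rule in section 4.2.4 with sections 4.2.2 and 8.2.2.

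The cost is some wording in sections 3, 4.2.4, 6.6 and 8.2.2, a little extra follow-up, one exclusion table and one sensitivity analysis. The rescue-free proportions may come out slightly less favourable. No rule on when rescue may be given changes.

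### The primary 1-hour analysis is labelled intent-to-treat but leaves out randomised patients who take rescue before 1 hour or give no 1-hour score, so the estimate may be biased in a direction the documents cannot settle

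*Combined protocol and SAP*

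**What the plan says.** Section 3 defines the primary outcome as "Mean change of pain score at 1 hour compared to baseline".

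Section 8.2.2 defines the intent-to-treat set by three conditions: more than 4 minutes of device use, and that the patient "did not take rescue medication before the 1 hour and reported pain at 1 hour". The same section states: "Imputation of missing data will be performed according to the last value carried forward method".

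Section 4.2.4, part a, gives the matching drop-out rules. On rescue in the first hour: "If the patient takes rescue medication before 1 hour, it is a drop-out", the reason being that "it is a drop-out because the action of the medication affects the pain estimate at 1 hour". On leaving: "If the patient stops the one-hour treatment and leaves the clinic, it is a drop-out". On device failure: "If the device stopped working accidentally, it is a drop-out because of technical reason". Section 6.6 goes slightly further, since there it is enough that the patient wants rescue during the hour.

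Two groups are treated differently. A patient who stops stimulation early but stays for the 2 hours is kept (4.2.4a). For rescue between 1 and 2 hours, 4.2.4b keeps the patient, and "the last value carried-forward method will be applied for 2 and 24 hours pain intensity estimate".

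Section 4.2.1 places randomisation before the device is applied, so every first-hour loss comes after randomisation.

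**The concern.** Taking rescue, or leaving, in the first hour is plausibly a consequence of pain that is not relieved or is getting worse. Excluding such patients conditions the primary comparison on something the treatment can influence. Each arm's mean is then taken over patients who reached a rescue-free 1-hour assessment, and the arms need no longer be comparable in the way randomisation made them.

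The stated reason, that medication contaminates the 1-hour score, justifies not using that score. It does not justify removing the patient.

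The imputation statement in 8.2.2 gives no protection. Everyone in the set has a 1-hour score by definition, so nothing can be carried forward for the primary outcome. The only additional analysis, per protocol, is narrower still, and no sensitivity analysis addresses these losses. At stake are the accuracy of the primary estimate and the justification for the intent-to-treat label.

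**Working it through.** **Inputs (8.2.1).** Assumed reduction at 1 hour: 59% verum, 10% placebo. Assumed differences: 2.83 at 1 hour and 2.40 at 2 hours. SD 2.42. Planned size: 45 per group. Assumed 24-hour rescue use: 71% placebo, 41.33% active. No first-hour loss rate is given anywhere, so all loss rates below are assumptions.

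**The plan's own figures.** A two-sided 5% two-sample t-test with 80% power and SD 2.42 needs 16.98, so 17 per group, for a difference of 2.40, and 13 for 2.83. A pooled two-proportion test of 71% against 41.33% needs 43. The stated 17 and 43 both reproduce.

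**Implied changes.**
- Baseline = 2.83 / (0.59 − 0.10) = 5.78. The 2-hour figures give a similar 2.40 / (0.55 − 0.14) = 5.85.
- Verum change: 0.59 × 5.776 = 3.41. Sham change: 0.10 × 5.776 = 0.58. Ratio 5.9.

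**Formula.** Let d_v and d_s be the shares of verum and sham patients lost before 1 hour. Suppose the planned changes hold in those who remain, and lost patients count as no change. Then:
- Difference with exclusion = 2.83.
- Difference with everyone counted = (1 − d_v) × 3.408 − (1 − d_s) × 0.578.
- Shift = d_v × 3.408 − d_s × 0.578.

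The second block of the table uses the ratio of the plan's 24-hour rescue rates, 71 / 41.33 = 1.72.

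| Verum loss | Sham loss | Shift (points) | Share of 2.83 | Difference, all counted |
|---|---|---|---|---|
| 2% | 2% | 0.06 | 2% | 2.77 |
| 5% | 5% | 0.14 | 5% | 2.69 |
| 10% | 10% | 0.28 | 10% | 2.55 |
| 20% | 20% | 0.57 | 20% | 2.26 |
| 2% | 3.4% | 0.05 | 1.7% | 2.78 |
| 5% | 8.6% | 0.12 | 4.3% | 2.71 |
| 10% | 17.2% | 0.24 | 8.5% | 2.59 |
| 0% | 10% | −0.06 | −2% | 2.89 |

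**When the sign changes.** The shift is zero when d_s / d_v equals the ratio of the true changes, which is 5.9 under the planning figures. A smaller true effect lowers this ratio. With sham change 0.578 and sham loss 1.72 times verum loss, exclusion overstates the effect only if the verum change exceeds 1.72 × 0.578 = 0.99, that is, a true difference above 0.42. If both arms truly change by the same amount c, the shift is c × (d_v − d_s): zero at equal loss, and an understatement if more sham patients are lost.

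**Scale.** The standard error of the difference is about 2.42 × √(2/45) = 0.51. A shift of 0.06 is about a tenth of that; 0.28 is a little over half.

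**Power with everyone counted, 20% loss in both arms.** Verum variance = 0.8 × 2.42² + 0.8 × 0.2 × 3.408² = 6.54, SD 2.56. Using this SD in both arms, which is conservative, 2.26 / (2.56 × √(2/45)) = 4.2, so power is above 98%.

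**The case against.** **First-hour rescue may be rare.** Section 6.6 allows no medication during the 2 hours and 4.2 offers rescue only at 2 hours, so rescue in the first hour would be a departure from the protocol. At 2% in each arm the shift is trivial. This limits the likely size, but the plan itself writes rules for the event, and rarity does not justify an exclusion linked to outcome.

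**The analysis is not restricted to treatment completers.** A reader might infer that it is. Section 4.2.4a keeps patients who stop stimulation early but stay. Accidental device stops are less clear: 4.2.4a calls them drop-outs, 8.2.2 does not list them as an exclusion, and 4.2.2 asks for a 60-minute score in any case.

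**Overstatement of the device effect is not established.** A reader might infer it from the 5.9 ratio. That ratio rests on setting a device pilot against the placebo arm of a separate drug trial. Nor does the background section supply a verum loss rate: its 10% is the share of attacks in which pain increased, in ten patients using 20-minute sessions, and is not a rescue rate. The only rescue figures by arm in the documents show more rescue on placebo, and they refer to 24 hours. This part of the objection stands in full.

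**Later time points are not handled uniformly.** Section 4.2.4b carries forward a measured 1-hour score, which is not the same as assigning baseline. Section 3 limits the later pain outcomes to patients without rescue, and 4.2.3 sets aside the 24-hour score after rescue. So 4.2.4b shows that the plan accepts carry-forward after rescue, but it is not a ready-made rule for the first hour.

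**Conclusion.** The concern holds in a limited form. The set called intent-to-treat excludes randomised patients for post-randomisation reasons plausibly caused by the outcome, and carry-forward cannot reach the primary outcome. The estimate may be biased, but the documents determine neither direction nor size.

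If the planning changes are right and losses count as no change, exclusion overstates the effect by 2% to 20% of 2.83 for equal losses of 2% to 20%. With sham loss 1.72 times verum loss, the figure is 1.7% to 8.5% for verum losses of 2% to 10%. The direction turns if sham loss exceeds 5.9 times verum loss, and at lower ratios if the true effect is smaller. A reader might infer that exclusion by itself creates a false positive; with no true difference, equal loss produces no bias. Nor is this a power problem. The plan should be corrected because the primary estimate otherwise depends on an unstated loss rate that no planned analysis examines.

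**What to change.** These changes concern the analysis only and leave the rules on medication use as they are.

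1. In 8.2.2, for the primary outcome, remove both conditions in "did not take rescue medication before the 1 hour and reported pain at 1 hour". Removing only the rescue condition would let the second exclude the same patients again, and would still lose those who leave the clinic. Analyse every randomised patient who passed the 4-minute tolerance step, in the allocated arm.
2. For rescue before 1 hour, or a missing 1-hour score, carry forward the last pre-rescue score. Section 7.1 schedules no score between baseline and 1 hour, so this is the baseline score and the change is zero.
3. Align the analysis wording of 4.2.4a and 6.6, including how accidental device stops are analysed.
4. Keep the present analysis as supportive, and report first-hour losses by arm and reason.
5. Add a sensitivity analysis that varies the change assigned to these patients separately in each arm, including worsening, to show where the conclusion would alter.

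**Cost.** Wording and one extra analysis. Baseline score and device number are already collected. The table in 7.1 schedules rescue recording only at 2 and 24 hours, so confirm that the case report form, which is not shown, captures first-hour rescue; the present definition of the set already needs that information. Single imputation is crude, which is why item 5 matters, and the estimated effect may come out somewhat smaller.
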